19.1. Subject Stopping Rules

1. Any event of DKA will result in withdrawal of subject from study.
2. Severe hypoglycemia secondary to subject non-compliance or other individual safety concerns:
 - Subject is not using the bolus wizard
 - Subject is not checking blood glucose using finger sticks
 - Subject is non-compliant with sensor wear
 - Subject is not following protocol procedures
 - Subject experiences a study pump malfunction

19.2. Stopping Rules for Entire Study

During the study period, the following steps will be taken for:

1. UADE
2. DKA
3. Severe hypoglycemia events that result in subject requiring paramedic assistance, an ER visit or subjects who experience seizure, coma or death:
 - Site will notify the sponsor on the same day after receiving knowledge of the event. If the event becomes known to the site after hours, then it should be reported to the sponsor the next day.
 - Sponsor will notify FDA and the country-specific regulatory agency in the EMEA region within 24 hours of knowledge of event and provide updates to those agencies as information becomes available.
 - Enrollment will be stopped after the above events have been reported
 - DSMB is to review the event within 48 hours from the time that sponsor is notified. If possible, the investigator should be available to answer questions by DSMB.
 - DSMB will provide recommendation to sponsor on the following:
 - If enrollment may resume
 - If the entire study has to be stopped, including subjects who have already received study devices.

20. Ethical and Regulatory Considerations

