Note 2: The term "life-threatening" in the definition of "serious" refers to an event in which the patient was at risk of death at the time of the event; it does not refer to an event which hypothetically might have caused death if it were more severe. (ICH Topic E 2 A Clinical Safety Data Management: Definitions & Standards for Expedited Reporting. EMEA 2006)

Serious Adverse Device Effect (SADE) (ISO 14155-2011)

Adverse device effect that has resulted in any of the consequences characteristic of a serious adverse event

Unanticipated Adverse Device Effect (UADE) (21 CFR 812.3(s)) equivalent to USADE (ISO14155-2011 3.42)

Any serious adverse effect on health or safety or any life-threatening problem or death caused by, or associated with, a device, if that effect, problem, or death was not previously identified in nature, severity, or degree of incidence in the investigational plan or application (including a supplementary plan or application), or any other unanticipated serious problem associated with a device that relates to the rights, safety, or welfare of subjects.

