16.7. Causality Assessment

An adverse event is not automatically related to the study device or procedure simply because the subject is wearing the device and participating in the study. The event should be reviewed to determine if the device or study procedure could have possibly caused the event and therefore is related to the study device or procedure.

Causality assessment is the determination of the relationship between an adverse event and the device being studied. A causal relationship is present if a determination is made that there is a reasonable possibility that the adverse event may have been caused by the device or a study procedure. It is expected

that the investigational center will review all elements surrounding the adverse event to properly assess the causality of the event to the study device or to a study procedure.

This review would include the subjects description of the event, study device uploads and medical records (if applicable) from the treating facility. These records will be made available to sponsor.

The following definitions should be considered when determining the relationship of the event to the device or study procedure:

Causal Relationship – clearly related to the device or procedure

Probable – likely related to the device or procedure

Possible – may be related to the device or procedure

Unlikely – doubtful that event is related to the device or procedure

Not Related – clearly not related to the device or procedure

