16.8. Anticipated or Unanticipated

If the adverse event is determined to be related to the study device or study procedure the Investigator must then assess the event to determine if it is anticipated or unanticipated.

- **Anticipated:** the event is identified in the CIP; labeling; report of priors or user guide.
- **Unanticipated:** the event has not been previously identified in the CIP; labeling; report of priors, Investigator brochure, or user guide.

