16.9. Severity of Event (Intensity)

A clinical determination of the intensity of the event will be made. The following guidelines should be used:

- **Mild:** transient, needing no special treatment, and/or does not interfere with the subject's daily activity.
- **Moderate:** low level of inconvenience or concern to the subject and may interfere with daily activities, but is usually improved by simple therapeutic remedy.
- **Severe*:** interrupts a subject's daily activity and typically requires intervening treatment.

*Please Note: In the classification of adverse events, the term “**severe**” is not the same as “**serious**.” The term “**severe**” relates to an indication of the intensity of a specific event (as in mild, moderate, or severe chest pain). The term “**serious**” relates to a participant/event outcome or action criteria, usually associated with events that pose a threat to a participant's life or functioning.

17. Data Safety Monitoring Board

A DSMB consisting of external physicians with an expertise in Endocrinology and the management of insulin requiring diabetes including CGM, along with an external statistician will be convened to review study progress, endpoints and safety.

The DSMB will perform a number of functions:

1. Adjudication of the following events:

- Serious Adverse Event
- Serious Adverse Device Effect
- Unanticipated Adverse Device Effect
- Severe Hypoglycemia

- Diabetic Ketoacidosis

The DSMB will assess these events to determine agreement or disagreement with the Investigator classification of the event. The Sponsor will notify the Investigator of any disagreement in assessment of an event by the DSMB. The DSMB will meet a minimum of every 6 weeks to adjudicate these events unless there are no events to adjudicate.

2. DSMB will track and trend the overall Safety of the study.

Incidence for the following will be reviewed by the DSMB:

- Incidence of all SAEs.
- Incidence of severe hypoglycemia
- Incidence of DKA
- Incidence of device related adverse events.

Applicable information for device related adverse events may include:

- Whether or not the event was unanticipated
- Review of sensor data from CareLink report (when applicable)
- Review of pump data from CareLink report (when applicable)
- Misuse of the device by the user

3. The DSMB will meet sooner if there is a DKA event, a UADE or a severe hypoglycemia event as outlined in the stopping rules for the entire study:

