- DSMB is to review the event within 48 hours from the time that the sponsor is notified. If possible, the investigator should be available to answer questions by DSMB.
- DSMB will recommend a decision to the sponsor on the following:
 - Whether or not enrollment will continue to be on hold
 - Whether or not the entire study will need to be stopped including for those subjects who have received study devices already.

4. The DSMB will provide a recommendation to the sponsor on whether or not pediatric subjects 2-4 years of age will be permitted to enroll into the study. The recommendation is based on a review of data from 10 subjects 5-6 years of age after they have completed the first month of the study period.

General guidance for DSMB's recommendations to sponsor should be based on the following:

Review of events may require the following information. Final disposition of an event may be delayed based on obtaining this information:

- Monitoring by sponsor at site
- Device return and failure analysis
- Carelink upload and review of Carelink reports
- Subject clarification to site regarding details about the event
- Source documents that support event: Paramedic records; ER records; Lab records; Hospital admission and discharge summary

The following factors should be carefully considered in the DSMB's recommendation to sponsor:

1. Was the severe hypoglycemia or DKA related to the HCL algorithm, SmartGuard with predictive threshold suspend or was it related to a known insulin pump risk? For example, a question that may

be considered in DKA would be whether the event was related to an infusion set issue or caused by the HCL algorithm.

2. Another important consideration would be if the severe hypoglycemia or DKA event was related to a device malfunction versus patient non-compliance. For example, if a software anomaly leading to an under-delivery of insulin is discovered versus the subject repeatedly ignoring alarms prompting the subject to take action.
3. Severe hypoglycemia or DKA caused directly by an infusion set issue when the study pump is functioning as intended would likely result in acceptance to proceed with the study versus severe hypoglycemia or DKA that are directly caused by the HCL algorithm or a device malfunction might stop study enrollment or entire study altogether.

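### The study-wide stopping rule has no clear all-cause death trigger: a death rated unrelated brings no mandated enrolment hold or 48-hour DSMB review, and for an unexplained death both can turn on the initial relatedness judgement

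*Protocol*

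**What the plan says.** Section 19.2 of the Protocol (Stopping Rules for Entire Study) lists three triggers: UADE, DKA, and "Severe hypoglycemia events that result in subject requiring paramedic assistance, an ER visit or subjects who experience seizure, coma or death". The synopsis carries the same list. A trigger starts a fixed sequence. The site tells the sponsor the same day (the next day if it learns after hours), the sponsor tells the regulators within 24 hours, enrolment stops, and the DSMB reviews the event within 48 hours of the sponsor being told.

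Section 17 item 3 restates the expedited classes: "The DSMB will meet sooner if there is a DKA event, a UADE or a severe hypoglycemia event as outlined in the stopping rules". For everything else that the DSMB adjudicates, including SAEs, section 17 item 1 sets the timing: "The DSMB will meet a minimum of every 6 weeks to adjudicate these events unless there are no events to adjudicate".

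Any death is an SAE under section 16.6, and section 16.3 requires SAEs to reach the sponsor within 24 hours. The UADE definition in section 16.6 covers a "life-threatening problem or death caused by, or associated with, a device" that was not previously identified. Relatedness is judged under section 16.7 and comes before anticipatedness. Section 16.8 says: "If the adverse event is determined to be related to the study device or study procedure the Investigator must then assess the event".

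**The concern.** The study's stated purpose is to show that the system is safe. The subjects are children from age 2, and section 20.1 classes the study as significant risk. In such a study one would expect every death to stop enrolment until the DSMB has looked at it. Here the automatic safeguard attaches to event classes, and a death has to be placed in one of them before it applies.

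For DKA and qualifying severe hypoglycemia, the protocol holds enrolment first and asks about cause afterwards. Section 17 gives the DSMB the question of whether the algorithm, an infusion set or non-compliance was responsible. For a death of unknown cause the order can be reversed, because someone must judge it related before the hold and the 48-hour review are required. A single recoverable DKA from a failed infusion set stops enrolment automatically, whereas a child's unexplained death might not.

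**Working it through.** The protocol gives no figure for this point and no sample size or error rate depends on it. The check is a cross-reading of the sections, followed by a comparison of the two review times.

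**1. Does trigger 3 cover every death?** The closing words of the item, on subjects with seizure, coma or death, can be read in two ways. They may list further outcomes of a severe hypoglycemia event, or they may stand alone. Two things favour the first reading: the words sit inside the numbered severe hypoglycemia item, and section 17 item 3 describes that class as a severe hypoglycemia event. The second reading would also make any seizure or coma, whatever its cause, a study-wide trigger. So death from any cause is not clearly covered.

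**2. A death rated unrelated.**
- UADE: not reached, because section 16.8 asks about anticipatedness only for related events and the definition needs a device association.
- DKA or severe hypoglycemia: not reached, if the death is attributed to something else.
- What is left: an SAE, with a 24-hour report to the sponsor (16.3) and DSMB adjudication on the routine schedule (17 item 1). No hold and no 48-hour review is prescribed.

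**3. An unexplained death.**
- DKA: section 16.5 asks for laboratory values and treatment in a health care facility. These are hard to obtain for a child found dead at home.
- Severe hypoglycemia: if no plasma glucose is available, section 16.5 accepts neurological recovery as sufficient evidence, which a death cannot supply. Other evidence, such as sensor data, may serve.
- UADE: open if the investigator judges the death related. Section 16.7 sets a low bar, namely that "there is a reasonable possibility that the adverse event may have been caused by the device or a study procedure", with a Possible category. The same section cautions: "An adverse event is not automatically related to the study device or procedure simply because the subject is wearing the device".

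If the first two routes cannot be confirmed, the hold and the 48-hour review rest on the initial relatedness judgement.

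**4. Mandated review times.**
- Trigger event: 48 hours ÷ 24 = 2 days from sponsor notification (19.2).
- Other death: the next routine meeting, at most 6 weeks × 7 = 42 days away if no ad hoc meeting is called (17 item 1).
- Ratio at the extreme: 42 ÷ 2 = 21.
- Enrolment hold: mandatory for a trigger, not prescribed otherwise.

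**The case against.** The strongest reply is that triggers aimed at the device's own harm mechanisms are a coherent choice and that the rest of the protocol leaves little uncovered. The UADE definition reaches events merely associated with a device and has a catch-all for other unanticipated serious problems bearing on subjects' safety or welfare. The relatedness threshold is low. The pump stores sensor glucose (section 2.1), and the causality review and the DSMB may both use device uploads. Every death reaches the sponsor within 24 hours, the DSMB may disagree with the investigator's classification, six weeks is only a minimum frequency, and section 20.7 requires principal investigators to assess whether to continue at their site. All of this stands and makes it unlikely that a suspicious death would be ignored. None of it mandates a hold or a 48-hour review.

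A second reply is that trigger 3, read broadly, already covers any death. That reading is grammatically possible, but section 17 item 3 points the other way. A rule on whether a child's death halts enrolment should not need interpretation.

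A reader might be tempted to go further in four ways that the documents do not support:

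- *Deaths escape as anticipated because Table 2 (section 20.4.1) lists death as a risk.* Table 2 lists death only as an outcome of hypoglycemia, and fatal severe hypoglycemia is already trigger 3. The hyperglycemia lists do not include it. A related death from another cause is therefore not made anticipated by Table 2.
- *A fatal case can never be shown to be severe hypoglycemia.* Section 16.5 makes neurological recovery sufficient evidence, not necessary evidence.
- *The 48-hour review itself may slip, given* "Final disposition of an event may be delayed based on obtaining this information". That sentence concerns the final disposition of events already under DSMB review. It delays neither the hold nor the first review.
- *The delay can be converted into children enrolled who should not have been.* A hold may be lifted after the 48-hour review, so the comparison is not with an indefinite stop. Enrolment means signing consent (section 10) and is followed by a run-in with Auto Mode off and six further days in Manual Mode. Entry of ages 2-4 is staged and the sponsor may guide the pace. A count of consents would not measure closed-loop exposure.

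**Conclusion.** The point holds as a cheap improvement to the safety rule. A death rated unrelated has no mandated enrolment hold and no mandated 48-hour review. A death that stays unexplained, and cannot be established as DKA or severe hypoglycemia, gets them only if it is initially judged related and classed as a UADE. Deaths classed as UADE, DKA or severe hypoglycemia are covered.

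The size is the difference in mandated timing: 2 days against up to about 42 days. The 42 days is an upper bound that assumes the death falls just after a routine meeting and that neither the DSMB nor the sponsor acts in between. The protocol permits such action but does not require it. The hold matters only while enrolment is open. The conclusion also assumes the narrow reading of trigger 3; on the broad reading, section 19.2 would cover every death and the remaining defect would be ambiguous wording there and in section 17 item 3.

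**What to change.** Add a fourth trigger, *any death, regardless of cause or relatedness*, to section 19.2, to the synopsis copy and to section 17 item 3, with the same notification, enrolment hold and 48-hour DSMB review as the other three. Reword trigger 3 so that seizure, coma and death are plainly outcomes of a severe hypoglycemia event. The DSMB can then release the hold quickly once a death is shown to be unrelated.

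The cost is a short edit in each of three places and, in operation, a rare extra DSMB call and a brief pause in enrolment for a death that proves unrelated. No endpoint, sample size or analysis changes.

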Subjects 2-6 years of age are not required to participate in a hotel study. Instead, they will participate in an out-of-home study for 5 consecutive days, 4-6 hours per day. During that 5 day period, subjects should engage in significant activity/exercise. Such activities could include utilizing gym play areas appropriate for toddlers and young children, swimming, and playground games. Evidence of geographic location and exercise/activity will be documented by daily photograph. In addition, investigational center staff will be present daily for the 4-6 hours of exercise during the 5 day period.

Auto Mode Frequent Sample testing

While in Auto Mode, subjects 7-13 years of age will undergo daytime and/or nighttime Frequent Sample Testing (FST) during the Hotel study with i-STAT® used as a reference value.

Subjects 7-13 years:

Overnight frequent sample testing (10PM to 7AM) in Auto Mode will be every 30 minutes; daytime frequent sample testing (7AM to 10PM) in Auto Mode will be every 60 minutes. The exact times of FST may differ, but the interval for testing should remain as described.

Subjects 2-6 years:

During one of the days of the out-of-home study subjects should undergo frequent sample testing for 4-6 hours using SMBG as a reference method. The frequent sample testing period will be supervised by investigational center staff. Frequency of testing is every 30 minutes. .

Note 1: The Auto Mode Frequent Sample Testing may be performed at any time during the hotel study (7-13 years) or the out-of-home study (2-6 years).

Note 2: It is important that calculation of total blood draw be maintained throughout the study so that the total amount of blood volume does not exceed the maximum each subject is allowed. If the maximum is reached, FST will be stopped.

All participating investigational centers will target 3-6 subjects (7-13 years) to undergo a hotel study on Day 7 to Day 14 in Month 1 of the study period. On Days 1-6 of the Study period, during which data necessary for Auto Mode initiation is collected, subjects will not be permitted to turn Auto Mode ON. Entry into Auto Mode will occur on day 7 whether at home or in hotel. A minimum of 4 subjects are recommended to participate in each of the hotel studies. However, the sponsor has discretion to allow more or less subjects to attend a hotel stay should the site request this.

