Each case book will contain all relevant Case Report Forms for each subject. Each subject will be assigned a unique 9-digit identifier that will be structured such that the first 3 digits correspond to the study number (XXX), the next 3 digits correspond to the investigational center number, and the final 3 digits correspond to the subject number. An example of a typical subject's unique identifier is shown in the following example: The numerical sequence XXX001001 translates into: Study number (XXX), investigational center number (001), Subject number (001).

All study documents, electronic Case Report Forms (eCRFs) and correspondence will use this identifier sequence in lieu of a subject's name or initials.

10. Informed Consent

Informed Consent/Assent will be obtained in accordance with the Code of Federal Regulations (CFR) Title 21, Part 50 (US only) or ISO14155:2011 (EMEA only). The Investigator or designee must obtain written informed consent/assent before any clinical study related activity takes place. Prior to entry into the study, the California Experimental Subject's Bill of Rights (if applicable), the IRB/EC and Medtronic-approved Informed Consent Form (ICF)/Assent form, and the Health Insurance Portability and Accountability Act

(HIPAA) Authorization Form (US only) will be given to each subject and legally authorized representative (if applicable). The Investigator or designee will fully inform the subject to subjects and parent(s)/guardian(s) of all aspects of the clinical study that are relevant to the subject's or parents'/guardians' decision to participate in the clinical study (e.g. purpose and duration of the study, requirements of the subject during the study, potential risks and possible benefits associated with participation in this study).

Subjects will be considered enrolled in the study upon signing the Informed Consent/Assent form(s)

All items addressed in the Informed Consent/Assent Form must be explained. The language used shall be as non-technical as possible and must be understandable to the subjects and parent(s)/guardian(s).

The subject and parent(s)/guardian(s) must have ample time and opportunity to read and understand the Informed Consent/Assent Form, to inquire about details of the clinical study, and to decide whether or not to participate in the clinical study. All questions about the clinical study should be answered to the satisfaction of the subject and parent(s)/guardian(s).

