- Failure to obtain informed consent prior to performing one or more study procedures.
- Failure to maintain ICFs on file for all subjects who have provided informed consent.
- Use of an ICF that has not received approval from the IRB/EC.

- Use of an incorrect version of the ICF.

- 11. **Study Visits – Enrollment and Run-In Period**
- 11.1. **Run-in Period Synopsis**

Run-In Period Synopsis (Visit 1-4)

The primary purpose of the run-in period is to allow study subjects to become familiar with the study devices and to assure they meet criteria for study participation. Subjects will also be asked to undergo overnight frequent sample testing to evaluate the *Low Management Suspend before Low* feature of the study pump at Run-in Visit 4. There is a window of 90 days from the end of Visit 1 to Visit 4 during which time subjects should complete run-in. If the run-in period is repeated an additional 30 days will be added to the run-in period window. If a repeat of the *Low Management Suspend before Low* testing is necessary, Sponsor discretion will be used to determine timing of the repeat.

Success criteria for run-in:

- Subject must have 3 or greater than 3 SMBG per day
- Subject must show sensor compliance (i.e. 2,880 glucose sensor data points equivalent to 10 days of sensor wear)
- Subject does **not** turn on the SmartGuard Low Management features before the *Low Management Suspend before Low* Frequent Sample Testing at Run-in visit 4
- Subject does **not** turn on the Auto Mode feature

The run-in period should be repeated if the subject does not meet all run-in success criteria as listed above or if the Investigator believes the subject needs to gain greater familiarity with study devices.

Subject should be withdrawn if they turn on the Auto Mode feature during this period.

• **Devices Worn:**

- Subjects are trained on all study devices prior to receiving them
- Subjects 2-13 years of age: Sensor is inserted by subject or with assistance from parent(s)/guardian(s)/companion(s) into either the abdomen or buttocks and connected to GST3C Transmitter

• **Calibration Requirements with Study Meter:**

- Approximately 30 minutes to 2 hours after the Sensor is initialized, the Study Pump will alert the user to enter meter BGs to perform initial calibration
- After the first calibration, the user must calibrate the Sensor within 6 hours of the first calibration
- The user must calibrate when prompted by the study pump via the Smart Cal feature

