11.5. Study Period Visit Details

11.5.1. Office Visit 5 – Study Period Alignment Visit

The purpose of this office visit is to provide subjects and their parent(s)/guardian(s)/companion(s) with study devices and training. Subjects will wear the device in Manual Mode for 6 days prior to entering into Auto Mode at the hotel or at home. **The use of the Auto Mode feature during the first 6 days of the study period will not be permitted.**

11.5.2. Daily Surveillance for First 14 days During Auto Mode:

Review Pump uploads daily for first 14 days once **subject has entered Auto Mode (CL)**. Therefore, it is important to note the protocol timelines in order to understand when the subject will enter CL.

- Questions to ask when reviewing the report may include:
 - Is the subject's glucose control worse from baseline
 - Is the subject experiencing too much hypoglycemia – for example hypoglycemia at night
 - Is the subject checking glucose

Note: Subjects are required to perform the daily pump uploads during Hotel portions of this study as well

11.5.3. For subjects who are participating in Month 1 Hotel studies:

- Instruct subjects and their parent(s)/guardian(s)/companion(s) that they may not turn ON the Auto Mode function on the study pump prior to Day 7.

11.5.4. For subjects who are participating in Month 2 or Month 3 Hotel studies:

- Instruct subjects and their parent(s)/guardian(s)/companion(s) that they may not turn ON the Auto Mode function on the study pump prior to Day 7.

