4. It should be noted that the final determination of causality related to the HCL System or SmartGuard with predictive threshold suspend that is made by the DSMB may include additional factors which the members consider to be clinically relevant and important.
5. The DSMB may take into account the thresholds listed below for the number of subjects experiencing hypoglycemia requiring assistance from another person, hypoglycemia resulting in seizure or loss of consciousness or DKA to identify when the number of subjects experiencing these events exceeds the number that would be anticipated for the study population over the duration of this study. These thresholds should be interpreted with caution due to potential differences in study populations and study design.

Adverse Event	Reference Rate (<26 years old)	Reference Rate (≥26 years old)
Hypoglycemia requiring assistance from another person to administer oral carbohydrates, glucagon or other resuscitative actions	≤4 subjects experiencing one or more events during study ¹	≤7 subjects experiencing one or more events during study ¹
Low blood glucose resulting in seizure or loss of consciousness	≤2 subjects experiencing one or more events during study ²	≤3 subjects experiencing one or more events during study ³
DKA	≤ 3 subjects experiencing one or more events during study ²	≤ 2 subjects experiencing one or more events during study ³

The event thresholds for hypoglycemia requiring assistance from another person is derived from the JDRF study of continuous glucose monitoring and intensive treatment of type 1 diabetes. The event thresholds for low blood glucose resulting in seizure or loss of consciousness is derived from the rate reported in T1D Exchange Clinic Registry. The rates reported in these previous studies are adjusted for the 3 month study period with 130 expected subjects to determine the maximum number of subjects expect to experience one or more of these events during the study.

1. Juvenile Diabetes Research Foundation Continuous Glucose Monitoring Study Group, Tamborlane WV, Beck RW, Bode BW, Buckingham B, Chase HP, Clemons R, Fiallo-Scharer R, Fox LA, Gilliam LK, Hirsch IB, Huang ES, Kollman C, Kowalski AJ, Laffel L, Lawrence JM, Lee J, Mauras N, O'Grady M, Ruedy KJ, Tansey M, Tsalikian E, Weinzimer S, Wilson DM, Wolpert H, Wysocki T, Xing D. Continuous glucose monitoring and intensive treatment of type 1 diabetes. N Engl J Med. 2008 Oct 2;359(14):1464-76

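### The automatic hold after a trigger event stops the signing of consent, not first Auto Mode activation, so it prevents no new Auto Mode exposure during the 48-hour DSMB review

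*Protocol*

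**What the plan says.** The Synopsis and Section 19.2 list the same steps after a trigger event: the site reports to the sponsor, the sponsor notifies regulators within 24 hours, the hold takes effect, and the DSMB reviews within 48 hours of sponsor notification. The hold reads "Enrollment will be stopped after the above events have been reported". The DSMB then recommends whether enrollment may resume and "If the entire study has to be stopped, including subjects who have already received study devices". Section 17 item 3 frames the first question as "Whether or not enrollment will continue to be on hold".

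Section 10 fixes what enrollment means: "Subjects will be considered enrolled in the study upon signing the Informed Consent/Assent form(s".

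Auto Mode comes later. Section 11.1 requires, for run-in success, "2,880 glucose sensor data points equivalent to 10 days of sensor wear", and Section 4 describes a two-week run-in. Section 11.5.1 then says "Subjects will wear the device in Manual Mode for 6 days prior to entering into Auto Mode at the hotel or at home", and Section 4 adds "Entry into Auto Mode will occur on day 7 whether at home or in hotel". No passage defers that step while a review is open.

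For the affected child, Sections 18 and 19.1 require withdrawal after DKA, and Section 18 also after severe hypoglycemia.

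**The concern.** The plan already accepts that a trigger event justifies an automatic pause before its cause is known. Section 17 asks the DSMB to judge whether the algorithm or a device malfunction caused the event. While that question is open, the pause falls on a step more than two weeks before any Auto Mode exposure. A child on study-period Day 5 or 6 reaches Day 7 and activates the algorithm on schedule.

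After the last consent the hold has nothing to act on, although first activations may continue. Run-in may take up to 90 days, or 120 if repeated (Section 11.1), before the six Manual Mode days begin.

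This is a significant-risk pediatric study (Section 20.1) whose stated purpose is safety (Section 3). The automatic pause would do most good where new exposure begins.

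**Working it through.** **Time from consent to Auto Mode**

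- Reproducing the protocol's figure: 2,880 sensor points at one per 5 minutes (assumed interval) is 2,880 × 5 / 1,440 = 10.0 days, as Section 11.1 states.
- Minimum lag: 10 days of sensor wear + 6 Manual Mode days = 16 days.
- Nominal lag: 14 + 6 = 20 days.
- Review window: 2 days. The lag is 8 to 10 times as long, so a hold on consent blocks 0 first activations in that window.

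**Mean number of first activations per review**

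Assumption: starts are spread over about 180 days, because Section 6 expects enrollment to take about 6 months. The counts are 120 completers (Section 5), the 130 behind the DSMB thresholds in Section 17 ("The rates reported in these previous studies are adjusted for the 3 month study period with 130 expected subjects"), and a ceiling of 200 if every consented subject started.

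| Starters | Per day | Per 48 h | Chance of at least one, even starts: 1 − exp(−mean) |
|---|---|---|---|
| 120 | 120/180 = 0.667 | 1.33 | 74% |
| 130 | 130/180 = 0.722 | 1.44 | 76% |
| 200 (ceiling) | 200/180 = 1.111 | 2.22 | 89% |

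**Allowing for hotel groups**

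Section 4 targets 3 to 6 subjects aged 7–13 per site for a Month 1 hotel study within Days 7–14. A six-day stay in that window can begin only on Day 7, 8 or 9, so the members of a group reach Day 7 within about two days of each other. Take 15 sites and 120 starters, and count each group as one start occasion:

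- Groups of 3: 45 children in 15 groups, plus 75 single starters = 90 occasions. 90/180 × 2 = 1.0 per 48 h; 1 − exp(−1.0) = 63%.
- Groups of 6: 90 children in 15 groups, plus 30 single starters = 45 occasions. 45/180 × 2 = 0.5 per 48 h; 1 − exp(−0.5) = 39%.

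Clustering leaves the mean unchanged. It lowers the chance of any start in a given window and raises the number when one occurs.

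**Share of all exposed children**

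Each child has Day 7 to Day 96 = 90 days, or to Day 110 = 104 days, in Auto Mode. At steady state about 0.667 × 90 = 60 to 0.722 × 104 = 75 children are in Auto Mode at once (ceiling 1.111 × 104 = 116). First starters in a 2-day window are therefore 2/104 to 2/90, about 2% of those exposed.

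**The case against.** The strongest reply is that nothing here is misstated. The protocol never says that the enrollment stop is meant to prevent first activation; it sets a staged response in which the DSMB decides about children with devices within 48 hours. That stands: this is a badly placed safeguard, not a contradiction.

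Controls also exist:

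- daily review of uploads for the first 14 days in Auto Mode (Section 11.5.2);
- daily calls on Days 7–13 for the Month 2 and 3 cohorts (Section 8.2);
- a staffed stay for Month 1 hotel groups (Section 11.5.5);
- a nighttime companion and a fixed alarm at 50 mg/dL (Section 4);
- withdrawal at the investigator's discretion (Section 18) and immediate-hazard deviations (Section 20.11).

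These reduce the stakes. But the monitoring measures act once the child is in Auto Mode, and the discretionary powers work case by case. None is a study-wide pause.

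A further reply is that deferring about 2% of exposed children protects few, and that some triggers, such as an infusion-set DKA, have nothing to do with Auto Mode. Both are true. Still, delaying a first activation keeps a child in the mode already in use. Taking Auto Mode away from children established on it is a different decision, properly left to the DSMB.

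A reader might infer that the hold is the only automatic consequence of any kind, or that children with devices are left outside the safety process. The documents do not support either: the affected child is withdrawn after DKA or severe hypoglycemia, and the DSMB can recommend stopping everyone.

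**Conclusion.** The point holds at study level and for children other than the affected one. As written, the automatic hold prevents no first Auto Mode activation during a review of up to 48 hours, and it restricts no one once consenting has ended. This follows from the protocol's own definition of enrollment and its own timeline, without distributional assumptions.

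The size is modest and does rest on assumptions. With starts over about 180 days, the mean is 1.3 to 1.4 first activations per full 48-hour window, with a ceiling of 2.2; a quicker review would see fewer. It is tempting to say that about three reviews in four would see a new activation. That needs evenly spread starts, which the Month 1 hotel plan makes unlikely. The supportable range is about 39% to 76%, and the usual outcome is none, one, or a hotel group. This is a cheap improvement worth making, not a serious flaw.

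**What to change.** In the Synopsis, Section 17 item 3 and Section 19.2, state: *From the report of a trigger event until the DSMB gives its recommendation, no new subject is consented and no consented subject activates Auto Mode for the first time. Day 7 activation is deferred and Manual Mode continues, with Suspend Before Low recommended. A hotel stay may begin in Manual Mode.* Add to the DSMB's list of recommendations whether consented subjects not yet in Auto Mode may activate it. The DSMB can then release the deferral at its 48-hour review when the event is plainly unrelated, even if final disposition must wait for records or device analysis.

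The cost is a delay of up to two days for about one to two children per event on average, and occasionally for a whole Month 1 hotel group, including after events that prove unrelated to Auto Mode. If five trigger events occurred while children were still starting (the Section 17 thresholds for the younger group: 3 subjects with DKA and 2 with seizure or loss of consciousness), that is 5 × 1.33 = 6.7 to 5 × 1.44 = 7.2 deferrals, with a ceiling of 5 × 2.22 = 11.1.

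The delay normally fits the 96–110 day window: Day 9 to Day 98 still gives 90 Auto Mode days. A Month 1 stay moved to Day 9 just fits Days 9–14 with no slack, so a slot may sometimes have to shift. Because frequent sampling may fall at any time in the stay (Section 4), starting the stay in Manual Mode will often avoid this.
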